PROTOCOL TITLE: Association between low bone density, vertebral fractures, and pain in sickle cell disease: an observational study

1) Protocol Title

Title: Association between low bone density, vertebral fractures, and pain in sickle cell disease: an observational study

Protocol Version Date: 05/19/23

2) Objective

To determine how low bone mineral density or vertebral compression fractures contribute to pain in a prospective cohort of adults with sickle cell disease

3) Background

Introduction

Sickle cell disease (SCD) is the most common inherited hemoglobin disorder in the world(1). SCD is considered an orphan disease in the United States (US) because it affects less than 200,000 people (2). SCD arises from a single nucleotide variant on chromosome 11 that encodes the β -globin gene. Under stressful physiologic conditions, red blood cells assume rigid, elongated shapes from sickle hemoglobin polymerization. Sickle erythrocytes, along with activated white cells and platelets, adhere to the vascular endothelium and impair blood flow downstream of the obstruction. Tissue ischemia and infarction ensues, eventually leading to end-organ damage (3). Therapeutic interventions like universal newborn screening, penicillin prophylaxis, vaccinations against encapsulated organisms, chronic red blood cell transfusions, and hydroxyurea therapy have transformed SCD from a genetic disorder with high childhood mortality to a chronic illness characterized by progressive pain and end-organ damage (4) .

SCD negatively impacts bone health. The skeletal system is repeatedly injured when recurrent hypoxia-reperfusion stress induces the release of cytokines that heighten bone resorption (5), while nutritional deficits, low muscle mass, delayed puberty and physical inactivity hinder bone formation (6-8). Skeletal complications of SCD (9) range from acute vasoocclusive bone pain, bone infarcts and osteomyelitis to more chronic manifestations, such as osteonecrosis, osteoporosis and vertebral deformities (10-13). Osteonecrosis, in particular, is a major cause of severe chronic SCD pain and significant permanent disability (14), which persist even after curative hematopoietic stem cell transplant (15).

Low bone density associates with osteonecrosis of the femoral head (or hip osteonecrosis) and pain in pediatric SCD. In collaboration with my co-investigators from the Sickle Cell Clinical Research and Intervention Program (SCCRIP), a lifespan prospective SCD cohort maintained at St. Jude Children's Research Hospital (16), we found that low bone density independently associates with hip osteonecrosis and chronic pain in pediatric SCD, see Table 1 (17). Generally, SCD complications progressively worsen with age. To support our hypothesis that therapies that improve bone health may also alleviate symptoms of hip osteonecrosis in adults, we first need to study the association between low bone density, vertebral fractures, and pain in a prospective cohort of adults with SCD.

Variable	Total cohort		HbSS/S β ⁰ -thalassemia subgroup	
	Adjusted OR (95% CI)	P	Adjusted OR (95% CI)	P
Adolescent category	7.7 (1.94-30.20)	.0037	4.7 (1.23-18.17)	.023
Hip osteonecrosis	4.0 (1.02-15.63)	.046	3.7 (0.69-20.11)	.13
Chronic pain	10.4 (1.51-71.24)	.017	9.3 (0.97-88.70)	.053
Hemoglobin	0.74 (0.57-0.96)	.022	NA	NA
Indirect bilirubin	NA	NA	1.4 (0.99-1.90)	.055

CI, confidence interval; NA, variable not selected in final model.

Table 1. Multivariable regression model of low bone mineral density in the SCCRIP pediatric cohort, excerpted from **Adesina et al.** *Blood Adv.* 2019 May 14;3(9):1476-1488.

PROTOCOL TITLE: Association between low bone density, vertebral fractures, and pain in sickle cell disease: an observational study

4) Inclusion and Exclusion Criteria

All adults with SCD who have received hematology care at UC Davis Medical Center (UCDMC) and non-UC Davis facilities will be assessed for potential eligibility. All eligible study participants will undergo a dual energy X-ray absorptiometry (DXA) scan to determine their baseline bone mineral density. The DXA instrument can also be programmed to obtain morphometric thoracolumbar spine X-ray to evaluate for the presence and severity of vertebral compression fractures. In addition to routine study labs, a small aliquot of fasting blood and urine samples will be collected from each study participant for biomarker analysis. Routine study labs can be drawn up to one week before or after the study visit. Fasting labs for biomarker analysis must be collected between 7:30-10am on the day of the study visit to account for changes due to the circadian rhythm.

Inclusion Criteria

- Age \geq 18 years with SCD (any genotype, confirmed by HPLC or hemoglobin electrophoresis)
- Ability to provide written informed consent
- Ability to lay on a DXA scanner
- Negative urine pregnancy test for women of childbearing potential at study entry

Exclusion Criteria

- Pregnant women
- Adults unable to consent
- Individuals who are not yet adults (infants, children, teenagers)
- Prisoners
- Hospitalizations (any cause) within 2 weeks of study entry

5) Study Timeline

This cross-sectional observational study involves obtaining a baseline DXA scan, vertebral fracture analysis (VFA) and pain assessment using the Adult Sickle Cell Quality of Life Measurement System (ASCQ-Me). We plan to recruit 50 subjects and anticipate enrolling 4 adults with SCD per month from Nov 2022– Dec 2023. Our goal is to complete primary data analysis by Mar 2024.

6) Study Endpoints

- To determine the association between bone density Z-scores and ASCQ-Me pain impact scores in adults with SCD.
- To study the association between Spine Deformity Index scores (SDI, a proxy for vertebral fracture analysis) and ASCQ-Me pain impact scores in adults with SCD
- To assess the correlation between baseline hematological and biochemical laboratory parameters; including bone biomarkers, and skeletal morbidity in a prospective cohort of adults with SCD

7) Procedures Involved

We hypothesize that adults with SCD and low bone density or vertebral compression fractures—adjusted for sex, SCD genotype, vitamin D levels and SCD-modifying therapies—will report more severe pain than those with normal bone density or no vertebral fractures. ASCQ-Me is a validated patient-reported outcome measure of

PROTOCOL TITLE: Association between low bone density, vertebral fractures, and pain in sickle cell disease: an observational study physical, mental, and social health in adults with SCD (18, 19). For biomarker analyses only, 30cc of whole blood and 10cc of urine will be collected from each study participant once (at baseline), after an overnight fast.

Methods: We identified 113 adults with SCD (58% female) followed at UCDMC from Oct 2017- Jul 2021. Using the National Institutes of Health (NIH) Toolbox iPad App, we will electronically administer the ASCQ-Me pain domain questionnaire to 50 ambulatory adults with SCD and securely store their responses on the Research Electronic Data Capture System (REDCap).

ASCQ-Me uses a T-score metric with a mean score of 50 for the reference population and a standard deviation (SD) of 10. We hypothesize that ASCQ-Me pain impact scores will directly correlate with lumbar spine, hip, forearm, or whole body bone density Z-scores; and inversely correlate with SDI scores (Figure 1).

Potential Problems/Alternative Strategies. Recruiting and retaining 50 adults with SCD is feasible within the study period. As previously noted, I am a co-investigator and co-chair the Bone Working Group in SCCRIP, the longitudinal study of 1300 children and adults with SCD maintained at St. Jude Children's Research Hospital. In the unlikely event that we are unable to recruit all 50 participants from UCDMC and non-UC Davis facilities, we will extend our study recruitment to include eligible adult participants from the SCCRIP cohort. For study participants who are not comfortable with using research iPads, we plan to administer the ASCQ-Me pain questions on paper in standard (13 questions) or short form (5 questions). A copy of the ASCQ-Me Pain Impact short form is excerpted below:

[figure not shown]

Figure 1. Study schema

PROTOCOL TITLE: Association between low bone density, vertebral fractures, and pain in sickle cell disease: an observational study

ASCOQ-Me® v2.0 Pain Impact - Short Form

Pain Impact - Short Form

Please respond to each question or statement by marking one box per row.

		Never	Rarely	Sometimes	Often	Always
PainImpact02	In the past 7 days, how often did you have pain so bad that you could not do anything for a whole day?	 5	 4	 3	 2	 1
PainImpact07	In the past 7 days, how often did you have pain so bad that you could not get out of bed?	 5	 4	 3	 2	 1
PainImpact08	In the past 7 days, how often did you have very severe pain?.....	 5	 4	 3	 2	 1
PainImpact09	In the past 7 days, how often did you have pain so bad that you had to stop what you were doing?.....	 5	 4	 3	 2	 1
PainImpact012	In the past 7 days, how often did you have pain so bad that it was hard to finish what you were doing?.....	 5	 4	 3	 2	 1

8) Data and/or Specimen Management and Confidentiality

- I understand that if this study involves the use of the UC Davis Health Electronic Health Record (EMR/EPIC), which also contains the clinical data for Marshall Medical Center (MMC). I understand that MMC patient data cannot be accessed for research purposes and that I must take the necessary steps to ensure that MMC data is not accessed, used, or disclosed for UC Davis Health research purposes.
- I understand that if this study involves use of UC Davis students' educational records (including records in the PI's own possession such as course exams/assignments), I must consult with the Registrar's office to see if all requirements of the Family Educational Rights and Privacy Act (FERPA) are satisfied. N/A

Data analysis plan and Power calculations:

To test the association between ASCQ-Me pain scores and bone density Z-scores, we will build a linear regression model with ASCQ-Me pain scores as the outcome of interest and bone density Z-scores as an independent variable. We will repeat the analysis using SDI scores and laboratory parameters as independent variables. We will further adjust for potential confounders, such as age, sex, SCD genotype, vitamin D levels and SCD-modifying therapies i.e, hydroxyurea use or chronic red blood cell transfusions. Then, we will add osteonecrosis in any joint (yes vs no) into the linear regression model to test the interaction between osteonecrosis and low bone density on ASCQ-Me pain scores, adjusted for the previously mentioned covariates. We will also test for the interaction between osteonecrosis and vertebral fractures on ASCQ-Me pain scores. For statistical power calculations only, we will categorize study subjects as being in group A (low bone density or vertebral compression fractures) and group B (normal bone density or no vertebral fractures) to better estimate the differences in pain scores observed between both groups. If we assume 50% prevalence of low bone density or vertebral fractures in adults with SCD ((12)18-20), then 50% of our study subjects will fall in group A and group B. If we assume mean pain scores of 40 in group A (i.e., one SD worse than the average population) and mean pain scores of 50 in group B (population mean), then enrolling 40 adults with SCD provides approximately 80% power to detect a statistically significant and clinically useful difference in ASCQ-Me pain impact scores between groups A and B (2-sided, alpha of 0.05; SD 10). We will enroll an additional 10 adults to account for study

PROTOCOL TITLE: Association between low bone density, vertebral fractures, and pain in sickle cell disease: an observational study discontinuations and to support exploratory endpoints e.g., interaction between low bone mineral density or vertebral compression fractures, osteonecrosis, and sickle cell pain.

Procedures for maintenance and confidentiality:

- This research study will include a Partial Waiver of HIPAA Authorization for participant identification and recruitment through medical chart review.
- A signed HIPAA Authorization will be required for access, use, or disclosure of identifiable private information for participation in research activities.
- All study data will be securely stored on password-protected REDCap system, which can only be accessed through institutional computers with encryption.
- The PI and research coordinator will complete a weekly audit to ensure all study data are collected/securely stored until study completion.

9) Data and/or Specimen Banking:

All patient data and biospecimens will be securely stored for at least 5 years after study completion to allow time for full data analyses.

10) Provisions to Monitor the Data to Ensure the Safety of Subjects

Every research team member will complete training in the Human Research Protections and Good Clinical Practice for Clinical Trials with Investigational Drugs and Biologics, through the Collaborative Institutional Training Initiative (CITI Program). The PI will monitor all research activities. The research will also be regulated by UC Davis's Institutional Review Board (IRB). The written consent forms include 24-hour physician contact information for any study-related emergencies. Any protocol deviations or study participants' safety concerns will be promptly reported to the UC Davis IRB and to the study sponsors.

11) Withdrawal of Subjects

The principal investigator (PI) is a board-certified hematologist with expertise in sickle cell disease, who will oversee all research activities and closely review all reported adverse events with the clinical research staff.

12) Risks to Subjects

The proposed research study confers minimal risk of harm to the study participants. SCD patients enrolled in the study will undergo a DXA scan to measure their bone mineral density, which will expose them to small doses of ionizing radiation with attendant risk. While still in the DXA scanner, they will be repositioned to obtain a lateral thoracolumbar spine X-ray for vertebral fracture analyses (VFA). The amount of radiation exposure received from the DXA and VFA scans fall below levels that are thought to result in a significant risk of harmful effects. They will also be asked to give blood and urine samples for biomarker analysis, and fill out the ASCQ-Me pain impact questionnaire.

Dual energy X-ray absorptiometry (DXA): We will perform one DXA scan for this study. Study participants will be exposed to a very small amount of X-ray radiation (less than 0.01mSV) during the DXA procedure(20). There are no known risks associated with radiation exposure levels this low. There may be some side effects with repeated exposure to radiation, including an increased risk of cancer. However, exposure to doses several thousand times greater than that obtained from this study would be required before an increased risk of cancer could be detected. Thus, the radiation exposure from this procedure represents a negligible health risk. Pregnancy testing will be performed prior to the DXA scan.

PROTOCOL TITLE: Association between low bone density, vertebral fractures, and pain in sickle cell disease: an observational study

Study subjects may experience discomfort while being positioned on the DXA scanner. The exercise physiologist conducting the study is well trained and will be instructed to position study subjects as quickly as possible to minimize any physical discomfort.

Vertebral fracture analysis (VFA): The DXA machine can be programmed to obtain a lateral spine X-ray of VFA scan. Similar to the DXA scan, patients will be exposed to a very small amount of X-ray radiation (0.05 mSV) during the VFA scan (20). There are no known risks associated with radiation exposure levels this low. There may be some side effects with repeated exposure to radiation, including an increased risk of cancer. However, exposure to doses several thousand times greater than that obtained from this study would be required before an increased risk of cancer could be detected. Thus, the radiation exposure from this procedure represents a negligible health risk. As above, pregnant patients will not undergo a VFA scan. The exercise physiologist conducting the study will reposition study subjects in the DXA scanner as quickly and as comfortably as possible to minimize any discomfort from this additional scan.

Specimen collection: The needle stick from a venipuncture (blood draw) may hurt. There is a small risk of bruising and fainting, and a rare risk of infection. Some SCD patients have indwelling port catheters for vascular access, which may also be used for blood collection. Venipuncture or accessing a port may be temporarily uncomfortable. Urine sample collection might also be inconvenient for some patients.

13) Potential Benefits to Subjects

We do not anticipate any direct benefits to study participants. If any study participant is found to have osteoporosis (a severe form of bone loss) on the DXA scan, they will be referred for additional work-up and appropriate treatment.

14) Multi-Site Research: N/A

15) Community-Based Participatory Research: N/A

16) Sharing of Results with Subjects

Study results may be shared with subjects, upon request. [name] (PI) will present preliminary and final results of all aspects of her proposed study at local and national meetings, including the NHLBI Annual Sickle Cell Clinical Research Meeting and the American Society of Hematology annual research meeting. She will publish her findings in peer-reviewed journals and share the results with the public through SCD advocacy groups and organizations.

17) Prior Approvals

This research is being funded by the **National Institutes of Health/National Heart, Lung and Blood Institute (NIH/NHLBI)** and the **Doris Duke Charitable Foundation (DDCF)**, who will provide additional research oversight.

PROTOCOL TITLE: Association between low bone density, vertebral fractures, and pain in sickle cell disease: an observational study

18) Provisions to Protect the Privacy Interests of Subjects

This study confers minimal risk of a confidentiality breach. We will apply appropriate data security measures to prevent unauthorized access to individually identifiable data

19) Compensation for Research-Related Injury

This study confers minimal risk of research-related injury as the DXA scan related to the study will only expose study participants to minimal radiation. Given the limited scope of this observational study, the University of California and the study Sponsors will cover any necessary medical treatment for study-related injuries, but they will not provide any other form of compensation for study-related injuries.

20) Economic Burden to Subjects

Study participants will be compensated \$100 for their time and effort. They may be asked for their social security number for payment purposes. It will not be used for any other purpose without their permission. In addition to the \$100 compensation, all study participants will be reimbursed for mileage (travel to and from study visit) parking, and other travel-related expenses for this research study visit. Since study participants will be fasting for the study, they will also be offered a meal voucher to use at the UCDMC cafeteria after their study visit.

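### The stated inputs give about 87% power with 40 adults, not about 80%, and group B is not worded as the complement of group A

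*Combined protocol and SAP*

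**What the plan says.** The sample size is justified once, in Section 8 of the protocol, under the data analysis plan and power calculations.

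- **Groups.** "For statistical power calculations only, we will categorize study subjects as being in group A (low bone density or vertebral compression fractures"), set against "group B (normal bone density or no vertebral fractures").
- **Split.** A 50% prevalence is assumed, and "then 50% of our study subjects will fall in group A and group B".
- **Effect.** The plan assumes "mean pain scores of 40 in group A (i.e., one SD worse than the average population") and a mean of 50 in group B.
- **Error rate and spread.** "2-sided, alpha of 0.05; SD 10". Section 7 supports the SD: "ASCQ-Me uses a T-score metric with a mean score of 50 for the reference population and a standard deviation (SD) of 10".
- **Result.** "then enrolling 40 adults with SCD provides approximately 80% power".
- **Extra subjects.** "We will enroll an additional 10 adults to account for study" discontinuations; the sentence goes on to give exploratory endpoints as a second purpose. This brings the total to the 50 in Section 5. No discontinuation rate is given.

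The planned analysis in the same paragraph is a linear regression of pain score on bone density Z-score. It is repeated with the Spine Deformity Index and with laboratory parameters, then adjusted for age, sex, genotype, vitamin D and disease-modifying therapy. The power statement names no test and does not say whether adjustment is allowed for.

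**The concern.** A two-group comparison of means needs the difference, the SD, the alpha, the sidedness and the group sizes. The paragraph gives all of them, so its power figure should be reproducible. A difference of one full SD with 20 per group should give clearly more than 80% power.

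The group definitions raise a separate question. Going from a 50% prevalence of group A to half the subjects in each group works only if group B is everyone not in group A. As worded it is not.

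The risk to the study is small, because an understated power does not leave it too small. What suffers is the only sample-size justification in the protocol. A reader who cannot reproduce it cannot tell whether 80% is a slip or a deliberate margin, for instance for the covariates in the planned models.

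**Working it through.** **Inputs, all from Section 8.** Difference 50 − 40 = 10; SD 10; standardised difference d = 10/10 = 1; two-sided alpha 0.05; N = 40 split 20 and 20.

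**The plan's figure.** For a two-sample t-test, the noncentrality is d × √(n₁n₂/(n₁ + n₂)) = 1 × √(20 × 20/40) = √10 = 3.162, with 40 − 2 = 38 degrees of freedom and a critical value of 2.024. The noncentral t distribution gives power of **86.9%**. The normal approximation gives Φ(3.162 − 1.960) = 88.5%, further from 80%. The stated figure is not reproduced.

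**The size that gives 80%.**

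| Per group | Total | Power (t-test) |
|---|---|---|
| 16 | 32 | 78.1% |
| 17 | 34 | 80.7% |
| 20 | 40 | 86.9% |
| 25 | 50 | 93.4% |

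The figure for 50 assumes that all are evaluable and evenly split; with 20 and 30 it is 92.4%.

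**What 40 adults detect with 80% power.** Solving for d with 20 per group gives 0.909. That is a difference of 9.1 points at SD 10, or an SD of 11.0 at a difference of 10 points.

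**Explanations that keep the stated alpha, split and N.** None reaches 80%.

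- A one-sided test gives 92.8%, which moves away from 80%.
- A Wilcoxon test with normal data gives about 85.3%.
- Spending 5 to 8 degrees of freedom on covariates, with nothing else changed, gives 86.4% to 86.6%.
- Treating the comparison as a correlation (r = 0.447, Fisher z) gives 83.3%.

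**Explanations that need an input the protocol does not state.** These do reach about 80%, but each is an assumption.

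- A 12 and 28 split: noncentrality √(12 × 28/40) = 2.898, power 80.6%. This contradicts the stated even split.
- Two-sided alpha of 0.025: 79.3%. This contradicts the stated 0.05.
- A 20% loss out of the 40, leaving 32: 78.1% by t-test, 80.7% by normal approximation.
- Covariates that explain a share R² of the variance in group membership and none of the variance in pain: noncentrality 3.162 × √(1 − R²). At 38 degrees of freedom, R² of 0.10, 0.15 and 0.20 gives 83.2%, 81.1% and 78.7%. With 5 to 8 covariate degrees of freedom, power is 80% at R² of 0.162 to 0.167.

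**Group definitions.** Group A is low density or fracture, so its complement is normal density and no fracture. With group B as worded:

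| Density | Fracture | Meets A | Meets B |
|---|---|---|---|
| Low | Yes | Yes | No |
| Low | No | Yes | Yes |
| Normal | Yes | Yes | Yes |
| Normal | No | No | Yes |

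The two middle rows fall in both groups, so a 50% prevalence of A does not fix the share in B.

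**The case against.** The strongest reply is that 86.9% belongs to an unadjusted t-test, which the protocol never names, while the planned analysis is an adjusted regression. A modest association between covariates and group membership would bring 40 adults to 80%, so the authors may have built in a margin. It can be added that the sentence speaks of enrolling 40, not of 40 evaluable adults; that the additional 10 serve two purposes with no stated division; and that 32 evaluable adults, a 20% loss from 40, give close to 80%. Raising the headline to 87% could then remove a useful margin. Read as at least 80%, the statement is true.

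Part of this stands. The documents cannot show whether the figure is a slip or an allowance, and a remedy that keeps 80% with its basis stated is legitimate. The rest does not rescue the text. No allowance is written down, discontinuations are assigned to the extra 10, and a gap of about 7 percentage points is more than rounding.

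On the groups, the intended complement can be guessed from the sentence about the split. The wording might also be meant pairwise: low against normal density, and fracture against no fracture. The Section 7 hypothesis uses the same or. These points make it a matter of clarification, but as written the definitions still overlap.

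**Conclusion.** The concern holds and is minor. On the stated inputs, power with 40 adults is 86.9%, about 7 percentage points above the figure given, and 34 evaluable adults would be enough for 80%. This rests on an unadjusted two-sample t-test, a common SD of 10, an even split and 40 evaluable adults. It says nothing about the power of the adjusted regressions or the interaction tests. The discrepancy is conservative, so the planned enrolment is not put in doubt under these assumptions.

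The group B wording is a separate, smaller point. It leaves the even split undefined for adults with only one abnormality. It does not affect the results, because the groups are used for the power calculation only and the regressions use Z-scores and Spine Deformity Index scores.

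**What to change.** In the Section 8 power paragraph, do one of the following:

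- **Restate the figure.** Say that 40 evaluable adults, 20 per group, give about 87% power for a 10-point difference (unadjusted two-sample t-test, two-sided alpha 0.05, SD 10), or 80% power for about 9.1 points.
- **Keep 80% and give its basis.** Name the test and state the allowance that yields it, such as covariate adjustment or an unequal split, with its assumed size. This is the right choice if a margin was intended.

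If a figure for 50 adults is added (about 93%), say that it holds only if all 50 are evaluable and evenly split.

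In the same paragraph, define group B as normal bone density and no vertebral fractures. No edit to the Section 7 hypothesis is proposed.

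The cost is rewording two sentences. Enrolment, analysis and hypothesis stay as they are.
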